**Table 1: Study Assessments - MV-NIS then Atezolizumab – Dose Escalation and Expansion Cohorts**

Tests and Procedures	≤21 days prior to registration	≤14 days prior to registration	Day 1	Day 3 ± 1 day	Day 8 ± 1 day	Day 15 +1 or -3 days 	Day 36 ± 1 day (Cycle 2/ Day 1)	Day 1 of Each Subsequent 21 Day Cycle	Follow-up 30 days after last dose of atezolizumab
Informed Consent	X								
Inclusion/Exclusion criteria	X								
Demographics	X								
Height	X								
History and exam  , weight, PS, vital signs	X				X	X	X	X	X
Hematology (see Table 2 )		X			X		X	X	X
Coagulation (see Table 2 )		X							X
Serum chemistry (see Table 2 )		X			X		X	X	X
Urinalysis (dipstick) (see Table 2 )		X			X		X	X	X
Pregnancy Test (see Table 2 ) 	X 								
Virology screen (HIV, HBV, HCV see Table 2 )	X								
Measles virus immunity (serum anti-measles IgG)	X*						X		
Tumor Measurement per RECIST 1.1 	X						X	X 	X 
SPECT/CT	X*				X				
Treatment (MV-NIS intratumoral injection)			X						
Treatment (Atezolizumab IV infusion) 						X	X	X 	
Concomitant medications	X→	X→	X→	X→	X	X→	X→	X	X→
AE assessment	X→	X→	X→	X→	X	X→	X→	X	X→
Tumor biopsy 	X*					X	X		
Viral shedding: mouth swab/ urine collection 	X*					X			
Blood: Paxgene Viremia 	X*			X		X	X		
Blood for exploratory analysis 	X*					X	X		

\* To be performed after registration but prior to study agent being given on Day 1.

[figure not shown]
1. Targeted physical exam only after baseline/screening.
2. For women of childbearing potential only. Must be done  $\leq$  7 days prior to registration.
3. Tumor assessments should be performed per RECIST 1.1, including confirmation of response at least 4 weeks later. irRECIST should be used for continuation of treatment decision in case of clinical stability with potential pseudoprogression/flare.
4. Atezolizumab will be administered every 3 weeks according to the approved US PI (Tecentriq 2016).
5. Biopsies to be obtained by radiologist under CT guidance. Pre-treatment biopsy will be of lesion planned for MV-NIS injection. Biopsy 12-15 days post-MV-NIS injection will be after SPECT/CT imaging but before atezolizumab administration and include 6 core biopsies of the MV-NIS-injected lesion and 6 core biopsies of an uninjected lesion (if feasible). See lab manual for further details and prioritization of processing in the case of insufficient material. Biopsies of injected lesion and an uninjected lesion may be repeated at day 36 (+/- 5 days) if feasible. Biopsies for a) paraffin sections, b) exome and RNA sequencing, c) infectious virus recovery, d) qRT-PCR for viral RNA. Exome sequencing only at baseline. See lab manual for details on processing and collection.
6. Mouth swab and urine collection for shedding studies by infectious virus recovery. See lab manual for details on processing and collection.
7. Assessment of viremia: Collect 2.5 ml blood into PAXgene tube (2 tubes). Perform at day 3, 15 and 36 (if day 15 is positive). If at day 36, there is 10-fold increase in MV-NIS/mcg of RNA, repeat tests will be performed within 2 days to confirm the result. Weekly testing will be done thereafter until resolution to baseline. See lab manual for details.
8. Research blood for a) immune phenotyping by flow cytometry, b) PBMC for exome and RNA sequencing, c) T cell analysis for neoantigen and tetramer assays. Exome sequencing done only at baseline. See lab manual for processing and collection.
9. Day 15 visit may be split into 2 visits to permit flexibility in biopsy timing and recovery prior to atezolizumab treatment as follows: Day 12-15 SPECT/CT, viral shedding, viremia, research blood for flow cytometry, PBMCs for sequencing and T cell assay must be performed PRIOR to tumor biopsy; Day 15-16 physical exam, history, vitals, PS and atezolizumab administration.
10. After Cycle 1, tumor measurements per RECIST 1.1 will be conducted every 3 cycles (i.e. cycles 4, 7, 10 etc.) until PD. For patients whose disease progresses, immune-related response criteria may be used by the investigator to continue therapy in the presence of potential pseudoprogression or tumor flare with clinical stability as appropriate until PD is confirmed.
11. Patients who discontinue atezolizumab for reasons other than disease progression will continue to have tumor evaluations every 12 weeks per standard of care until PD.

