PD evaluation	
Tissue analysis for MV-NIS: Tumor biopsy is to be performed by radiologist post virus injection according to Table 1. Samples will be stored in:
 
 
RNAlater® for quantitative RT-PCR for MV-NIS RNA to determine copy numbers of virus/µg cellular RNA and RNASeq®
 
frozen sections for exome analysis
 
formalin-fixed paraffin embedded (FFPE) for pathology analysis (H&E and immune marker IHC).
 
 
Tissue analysis for tumor microenvironment: Tumor biopsy FFPE slides will be stained for immune markers including but not limited to CD3, CD4, CD8, CD14, CD20, and PD-L1.
 
Assessment of neoantigens and tumor-specific immune response: whole exome sequencing and RNA sequencing will be performed from normal tissue (PBMCs) and tumor biopsy samples obtained before and ~2 weeks after MV-NIS injection. Detailed bioinformatics analysis will be undertaken to determine mutational/antigen profiles. Identification of candidate 9-10 amino acid peptides containing mutations predicted to bind with high affinity to patients' MHC Class I molecules will be done by using the Immune Epitope Database prediction algorithm. Chosen peptides will be synthesized and used to prepare MHC fluorescent tetramers for their use for flow cytometry of patient peripheral T cells and/or TILs to determine frequency of tumor specific T cells pre and post therapy. In addition, functional assays of T cells will be performed by IFN-gamma release assays.

Efficacy	
RECIST v1.1 will be used to assess anti-tumor efficacy for the secondary efficacy endpoint. An exploratory analysis using irRECIST will also be performed.
 
irRECIST will be used for defining progressive disease (PD) on study as follows to account for the possibility of pseudoprogression or tumor flare. Patients should be reevaluated for disease response every 9 weeks after cycle 1 (i.e. at end of cycles 4, 7, 10, etc).
 
For clinically stable patients, if imaging shows PD, treatment may be continued and tumor assessment should be repeated ≥ 9 weeks later to confirm or refute PD. Clinically stable is defined by the following criteria:

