### 6.3. Exploratory objectives

- To determine the time-course of viral infection, dissemination, and elimination through the measurement of NIS gene expression using SPECT/CT imaging.
- To assess viremia, viral replication, and viral shedding/persistence following intra-tumoral administration of MV-NIS and immunotherapy.
- To obtain preliminary data regarding the antitumor efficacy by serial measurements of radioiodine uptake by SPECT/CT, radiological ORR, DOR and PFS and to correlate with PD-L1 expression and other immune biomarkers.
- To characterize the peripheral blood immune phenotype, presence and peripheral blood repertoire representation of neoantigen-specific T cells, and cell-free DNA of patients at potential immunologic transition points including study enrollment, therapy initiation, during therapy, and at follow-up.
- To evaluate if therapy with MV-NIS, atezolizumab, or both alters the peripheral blood immune phenotype, presence and peripheral blood repertoire representation of neoantigen-specific T cells, or cell-free DNA.
- To characterize the tumor microenvironment by immunohistochemistry (IHC) for PD-L1 and other immune markers of interest on tissue prior to and at the completion of MV-NIS injection and following atezolizumab treatment.
- To evaluate if MV-NIS alter the pretreatment tumor microenvironment levels of PD-L1 or immune markers after therapy in the lesion injected with MV-NIS.
- To determine if lesions not injected with MV-NIS express comparable levels of PD-L1 or contain an immune marker milieu within the tumor microenvironment similar to the lesion injected with MV-NIS after treatment with MV-NIS and atezolizumab.

- To assess if changes to the circulating or tumor microenvironment immune biomarkers associate with clinical response.
- To evaluate the tumor genomic mutational burden by whole exome sequencing, level of neoantigen expression and signal transduction pathways by RNAseq prior to and after therapy with MV-NIS and atezolizumab.
- To determine if changes to the tumor genomic mutational burden, level of neoantigen expression or alterations in signal transduction pathways are associated with clinical response
- To assess the secondary efficacy parameters (ORR, DOR and PFS) using irRECIST in addition to classical RECIST 1.1.
- To compare PFS of the combination of MV-NIS and atezolizumab in patients with recurrent and metastatic NSCLC versus historical controls

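### Table 1 footnote 5 limits tumor exome sequencing to baseline, against the synopsis and the exploratory objectives on change in mutational burden; cell-free DNA is also missing from the schedule.

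*Combined protocol and SAP*

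**What the plan says.** **Exome sequencing.** Footnote 5 of Table 1 covers the tumor biopsies and states "Exome sequencing only at baseline". Footnote 8 covers the research blood and states "Exome sequencing done only at baseline". The synopsis (section 4, PD evaluation) says that whole exome and RNA sequencing will be performed on PBMCs as normal tissue and on "tumor biopsy samples obtained before and ~2 weeks after MV-NIS injection". The same row lists frozen sections for exome work among the storage formats for the biopsy taken after injection.

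Section 6.3, repeated in the synopsis, has two objectives that depend on this. One evaluates mutational burden by whole exome sequencing before and after MV-NIS and atezolizumab. The other begins "To determine if changes to the tumor genomic mutational burden" and relates those changes to clinical response.

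**Cell-free DNA.** Section 6.3 also sets out to characterize the peripheral immune phenotype, neoantigen-specific T cells and "cell-free DNA of patients at potential immunologic transition points including study enrollment, therapy initiation, during therapy, and at follow-up". Footnote 8 lists "Research blood for a) immune phenotyping by flow cytometry, b) PBMC for exome and RNA sequencing, c) T cell analysis for neoantigen and tetramer assays". Section 12.1.21 adds leukocyte fractions but does not mention cell-free DNA. Section 7.1.5 does say that correlative blood will be used for information on free DNA, without naming a visit or a tube. The Table 1 row "Blood for exploratory analysis" is marked at baseline, Day 15 and Day 36, and is blank for later cycles and for the 30-day follow-up.

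**The concern.** A change needs at least two measurements. Table 1 is the schedule that sites and laboratories work from, and its footnote permits only one tumor exome. I found no statement of which text prevails when the schedule and the synopsis disagree. A laboratory could follow footnote 5 in good faith and leave two stated objectives without data on mutational burden.

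The post-treatment tissue is collected in any case: 6 cores from the injected lesion at Day 12-15, and 6 from an uninjected lesion if feasible. If exome work is not expected on those cores, tissue may not be set aside for it when material is short. The cell-free DNA gap is smaller, but plasma not kept at a visit cannot be recovered later.

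**Working it through.** The plan gives no figure on this point and no formula applies. The check sets the texts side by side and counts time points.

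**Tumor exome**

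| Source | Tumor exome time points | Change estimable? |
|---|---|---|
| Table 1 footnote 5 | 1 (baseline) | No |
| Synopsis, PD evaluation | 2 (baseline, about 2 weeks) | Yes, for MV-NIS alone |
| Section 6.3 objectives | At least 2, the later one after both agents | Required |

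1. Under footnote 5 the number of patients with a post-treatment exome is 0, whatever the final sample size. Mutational-burden change is then missing for all 21 patients intended for efficacy evaluation at the MTD.
2. The objective specifies whole exome sequencing for mutational burden, and the plan offers no substitute assay. Neoantigen expression and signaling pathways in the same objectives rest on RNA sequencing, which footnote 5 does not restrict, so those components stand.
3. Footnote 8 is not part of the obstacle. The synopsis uses PBMCs as the normal-tissue comparator, and a single baseline PBMC exome does not block a comparison of tumor at two times.
4. Footnote 5 and section 12.1.18 place the Day 12-15 biopsy before atezolizumab. A Day 12-15 exome therefore shows the state after MV-NIS only. The only scheduled tumor sample after both agents is at Day 36, and it is optional.

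**Cell-free DNA**

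| Time point in section 6.3 | Research blood in Table 1 |
|---|---|
| Enrollment and start of MV-NIS | Baseline, after registration and before dosing |
| Start of atezolizumab | Day 15 (footnote 9 puts this draw before the biopsy, which itself precedes atezolizumab) |
| During therapy | Day 36 |
| Follow-up | None |

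There are 3 scheduled draws, none at follow-up, and no Table 1 entry names cell-free DNA. If the assay is run on these draws, as section 7.1.5 intends, change from baseline to Day 15 and to Day 36 can be measured. The follow-up time point has no sample for cell-free DNA, nor for the immune phenotype and T-cell measures named in the same objective.

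**The case against.** The strongest defense is that this is a drafting conflict and not a missing plan. The synopsis states two exome time points, the tissue is collected, and stored cores could be sequenced later. The lab manual, to which footnotes 5 and 8 defer for processing and collection, is not among the documents and may settle both the exome timing and the cell-free DNA tube. Table 1 is not exhaustive elsewhere either: its SPECT/CT row omits the conditional Day 15 and Day 36 scans of section 12.1.13. All the affected objectives are exploratory, and section 13.1.8 treats testing of correlative laboratory data across dose levels as hypothesis-generating.

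Most of this stands, and it limits the point. It does not remove the contradiction, because footnote 5 does not merely omit a post-treatment exome but excludes it.

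A reader might infer more than the documents support, in three ways:
- **That the exome objectives cannot be answered at all.** This holds only if footnote 5 prevails, and then only for mutational burden.
- **That cell-free DNA is unplanned and its objective unanswerable.** Section 7.1.5 plans it, and blood is drawn before and after treatment. What is missing is the entry in footnote 8 and section 12.1.21, and the follow-up sample.
- **That up to 24 + 18 = 42 patients are affected.** The two maxima do not go together. An expansion of 18 implies 21 - 18 = 3 patients at the MTD from escalation. An escalation of 24 means six at each of four dose levels, which leaves 21 - 6 = 15 for expansion. Replacement or re-enrollment could also change the total.

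**Conclusion.** The contradiction is real. Footnote 5 allows one tumor exome, the synopsis plans two, and the objectives need a change. If the footnote governs, no patient has a post-treatment exome and the mutational-burden component of two exploratory objectives cannot be estimated. If the synopsis governs, the effect of MV-NIS can be estimated, but the effect of the combination named in the objective still depends on optional Day 36 tissue.

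The secondary point also holds: cell-free DNA is planned in section 7.1.5 but not listed in the schedule or the procedures, and the follow-up time point has no blood sample.

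The conclusion assumes that no document outside those reviewed, such as the lab manual, overrides footnote 5 or names the cell-free DNA collection. Severity is low: the MTD determination, the ORR analysis and the RNA sequencing components are untouched.

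**What to change.** 1. **Footnote 5.** Change the exome time points to baseline and Day 12-15 tumor, in line with the synopsis. Leave footnote 8 at baseline only for the normal-tissue PBMC exome.
2. **Objectives.** Because the Day 12-15 biopsy precedes atezolizumab, either also sequence Day 36 tissue where it is obtained, or reword the before-and-after objective, and the change objective that follows from it, to the effect of MV-NIS. If no post-treatment exome is wanted, delete the change-in-mutational-burden component from section 6.3 and bring the synopsis into line.
3. **Cell-free DNA.** Add it to footnote 8 and section 12.1.21 at the existing baseline, Day 15 and Day 36 draws. Baseline is needed for any change to be computed.
4. **Follow-up time point.** Drop it from the objective, or add a research draw at the existing 30-day visit.

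Cost: no additional biopsy procedure. Items 1 and 2 cost the sequencing of cores already collected, or only a wording change. Item 3 is an aliquot from scheduled draws. The second option in item 4 is a new draw at an existing visit, a small extra cost. The lab manual should be checked against whichever version is adopted.

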### 5.2. Safety Profile of MV-NIS

To date, 16 patients have received intraperitoneal MV-NIS at doses of  $10^8$  or  $10^9$  TCID50 and 45 patients have received IV MV-NIS at doses of  $10^6$  to  $10^{11}$  TCID50. Twelve patients have received MV-NIS intrapleurally at doses from  $10^8$  to  $9 \times 10^9$  TCID50. The highest dose levels in all three routes of administration were recommended for further study. Six patients have received MV-NIS  $10^8$  TCID50 intratumorally with one DLT.

The most common related AEs (>1 patient) with intraperitoneal administration were all grade 1 and 2, in order of descending frequency: abdominal pain (50%), fatigue (37.5%), fever, neutropenia, leukopenia and flatulence (all at 19%), nausea, diarrhea and abdominal distension (all at 12.5%). There were no DLTs.

In the IV study, related grade 1-2 AEs seen in at least 5 patients were: nausea (n=10); chills and leukopenia (each n=8); fever (n=6); and diarrhea and neutropenia, (each n=5). Grade 3-4 AEs deemed at least possibly related to protocol therapy were: neutropenia (n=10); thrombocytopenia (n=5); anemia (n=2); and lymphopenia (n=1). One patient treated with cyclophosphamide and TCID50 9x10^7 had a grade 3 left ventricular failure possibly related to therapy. One grade 4 neutropenia was considered a DLT at the highest dose level (10^11 TCID50).

With intratumoral administration the only toxicities observed in more than one patient were anorexia, fatigue (both 33%) and lymphopenia (50%). There was 1/6 DLTs (grade 3 oral cavity fistula in non-injected tumor).

With intrapleural administration the most frequent toxicities were hematological including anemia, thrombocytopenia, leukopenia and neutropenia. There were no DLTs reported.

The [Investigator's Brochure](#) contains a summary of all MV-NIS-related AEs reported to date across the clinical trials, irrespective of route of administration.

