#### 7.1.1.1. DLT definition

DLT will be defined as an AE that is not pre-existing due to malignancy, attributed (definitely, probably, or possibly) to the MV-NIS, occurring within 36 days of MV-NIS administration and meeting the following criteria:

Hematologic:	$\geq$ grade 3 as per NCI Common Terminology Criteria for Adverse Events (CTCAE) v4.03 except grade 3 ANC lasting < 72 hours.
Renal:	Serum creatinine $\geq$ 2 times baseline.
Viremia:	Lasting for $\geq$ 4 weeks after intratumoral injection.
Clinical measles:	Any grade per CDC definition ( http://www.cdc.gov/measles/hcp/index.html )
Other non-hematologic, including:	$\geq$ grade 3 AE as per NCI CTCAE v4.03.
• Allergic reactions	
• Autoimmune toxicity	
• Organ toxicity	

Note: in the case of grade 3-4 laboratory abnormalities, and any other clinically significant lab findings which potentially meet the definition of DLT, repeat tests must be performed every 1-2 days in order to verify duration accurately and observe recovery.

AEs meeting these definitions but related only to atezolizumab will not be considered a DLT.

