### **7.1.2. Conduct of escalation cohorts**

A standard 3+3 design will be used for the dose escalation part of the study. Starting at dose level 1 (refer to [Table 3](#)), three patients will be treated per dose level. The first three patients treated at dose level 1 will be enrolled at least 24 hours apart. All patients will be observed for a DLT period of 36 days after MV-NIS administration (which is 3 weeks after atezolizumab) and the last patient in each cohort must have completed the DLT period prior to each dose escalation decision. Resolution of viremia in all patients at a dose level is required prior to dose escalation being allowed.

If a DLT is observed, 3 additional patients will be enrolled at that dose level. If 1/6 patients experiences DLT, escalation may proceed; if  $\geq 2/6$  patients experience DLT, the MV-NIS dose will be de-escalated and 3 further patients added at the previous dose level. Dose level -1 will only be explored if dose level 1 is not tolerated. Doses will not be escalated in any individual patient. Any patient who experiences a DLT will be taken off study drugs, but will be followed up for response and PFS.

If no DLTs are seen at any of the dose levels, then the MTD will be the maximum delivered dose ( $1 \times 10^9$ ). MTD will be defined as the highest safely administered dose at which no more than one out of six or 0/3 patients experience DLT.

The first 6 patients of the expansion cohort will be enrolled and observed for 36 days after the 6th patient has received treatment prior to any additional patients being treated. If  $\leq 1/6$  DLT is observed then the remaining patients will be enrolled and treated sequentially, with no waiting period or limitation on simultaneous enrolment. If  $\geq 2/6$  patients in the expanded cohort experience a DLT, then the entire expansion cohort will be re-enrolled at the next lower dose level.

If a patient fails to complete the initial course of therapy (defined as study drug administration and four weeks of observation) for reasons other than adverse events or disease progression based on the day 36 CT-scan, then the patient will be regarded as non-evaluable for DLT and an additional patient will be treated at the current dose level. However, all AE information from patients who received any study treatment will be utilized in the analysis.

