#### **5.2 Immune-Related Hepatitis**

Immune-mediated hepatitis, defined as requiring use of corticosteroids and with no clear alternate etiology, occurred in patients receiving TECENTRIQ treatment. Liver test abnormalities occurred in patients who received TECENTRIQ. Monitor patients for signs and symptoms of hepatitis. Monitor AST, ALT, and bilirubin prior to and periodically during treatment with TECENTRIQ. Administer corticosteroids at a dose of 1–2 mg/kg/day prednisone equivalents for Grade 2 or greater transaminase elevations, with or without concomitant elevation in total bilirubin, followed by corticosteroid taper. Withhold TECENTRIQ for Grade 2 and permanently discontinue TECENTRIQ for Grade 3 or 4 immune-mediated hepatitis [*see Dosage and Administration (2.2) and Adverse Reactions (6.1)*].

Across clinical trials (n=1978), Grade 3 or 4 elevation occurred in ALT (2.5%), AST (2.3%), and total bilirubin (1.6%).

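### No hematology or serum chemistry is scheduled between Day 8 and Day 36, including before the first atezolizumab infusion, so short silent laboratory DLTs can be missed

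*Combined protocol and SAP*

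**What the plan says.** Table 1 ("Study Assessments - MV-NIS then Atezolizumab") marks hematology and serum chemistry within 14 days before registration, on Day 8, on Day 36 (Cycle 2 Day 1), on Day 1 of each later cycle and at follow-up. The Day 1, Day 3 and Day 15 cells are blank in both rows, whereas the history and examination row does carry a Day 15 mark.

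Footnote 9 allows the Day 15 visit to be split. The first half is "Day 12-15 SPECT/CT, viral shedding, viremia, research blood for flow cytometry, PBMCs for sequencing and T cell assay must be performed PRIOR to tumor biopsy", and the second is "Day 15-16 physical exam, history, vitals, PS and atezolizumab administration". Neither includes a safety panel, although blood is drawn for viremia and research. Section 12.1.8 adds no time point.

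Under Section 7.1.2 patients are "observed for a DLT period of 36 days after MV-NIS administration (which is 3 weeks after atezolizumab"). The DLT criteria in Section 7.1.1.1 include grade 3 or higher hematologic events ("except grade 3 ANC lasting < 72 hours"), a doubling of baseline creatinine and grade 3 or higher organ toxicity. An event possibly related to MV-NIS is enough; only events related solely to atezolizumab are excluded.

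Sections 9.1.6 and 9.1.7 tie atezolizumab administration and modification to the label. The appended label, Section 5.2, says: "Monitor AST, ALT, and bilirubin prior to and periodically during treatment with TECENTRIQ".

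**The concern.** The primary objective is an MTD from a 3+3 design, so everything rests on a correct DLT call for each patient. Several DLT criteria can be met without symptoms and are then visible only in a blood test. A silent event that begins and resolves between two draws is recorded as no DLT, and that error always favors escalation.

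The blank at Day 15 looks like an omission, because both panels are marked at every later infusion visit and missing only at the first. Without that draw, the last scheduled virus-only value is a week old when atezolizumab starts, and an abnormality first seen on Day 36 follows exposure to both agents.

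The planned analyses are affected as well. Section 13.1.5 makes nadir or peak a main laboratory measure, and Section 13.1.8 foresees time to WBC, ANC and platelet nadirs. Within the DLT window these would rest on two scheduled post-injection values.

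**Working it through.** **Plan's own figure.** Day 15 + 21 days = Day 36, so the window's stated equivalence to three weeks after atezolizumab holds.

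**Size of the gap.** 36 − 8 = 28 days nominal. With ±1 day at each visit it is 35 − 9 = 26 to 37 − 7 = 30 days. The nominal time from the last panel to the first infusion is 15 − 8 = 7 days.

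**Detection model (assumed).** The documents give neither onset times nor durations. Assume that onset is uniform, an episode lasts *d* days, and only scheduled draws on nominal days count. An episode is seen if its onset falls in [draw − *d*, draw] for some draw. The share seen is the length of the union of these intervals divided by the onset range.

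For onset over Days 2-36 (34 days):

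| *d* | Draws on Days 8, 36 | Draws on Days 8, 15, 36 |
|---|---|---|
| 5 | (5 + 5)/34 = 29% | (5 + 5 + 5)/34 = 44% |
| 7 | (6 + 7)/34 = 38% | (6 + 7 + 7)/34 = 59% |
| 10 | (6 + 10)/34 = 47% | (13 + 10)/34 = 68% |

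The first entry is 29.4%, or about 30%. For *d* = 7 and 10, the Day 8 interval is cut off at Day 2 and contributes 6 days. For *d* = 10, the Day 8 and Day 15 intervals overlap and together cover Days 2-15, which is 13 days.

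For 7-day episodes with onset before atezolizumab (Days 2-15, 13 days), the planned draws see 6/13 = 46%. A Day 15 draw makes this 13/13 = 100%.

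For 7-day episodes with onset over Days 15-36, the share is 7/21 = 33% with or without a Day 15 draw.

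**Effect on the 3+3.** A dose level passes on 0/3 or 1/6, with probability (1 − q)³ + 3q(1 − q)⁵, where q is the detected DLT rate. Assume a true rate of 0.33, 7-day episodes, onset uniform over Days 1-36 (35 days), and a share *s* of DLTs that are silent laboratory events. The share of silent events seen is c = 14/35 = 0.40 as planned and 21/35 = 0.60 with a Day 15 draw. Then q = 0.33(1 − s + s·c).

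| *s* | q planned | Chance of escalating, planned | q with Day 15 | Chance of escalating, with Day 15 |
|---|---|---|---|---|
| 0 (full detection) | 0.330 | 43.4% | 0.330 | 43.4% |
| 25% | 0.281 | 53.5% | 0.297 | 50.0% |
| 50% | 0.231 | 64.1% | 0.264 | 57.0% |
| 100% | 0.132 | 84.9% | 0.198 | 71.3% |

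**The case against.** **The plan has safeguards.** Grade 3-4 abnormalities must be repeated every 1-2 days, unscheduled visits can include hematology and chemistry (Section 12.1.23), and the label asks for liver tests before treatment. These reduce the problem but do not remove it. Repeat testing needs a first abnormal value, unscheduled testing needs a reason to test, and the label passage covers liver tests only and fixes no Day 15 draw.

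**Onset may be early.** After a single injection, events may cluster in the first week. If all onsets fell in Days 2-8, the Day 8 draw would see 5/6 = 83% of 5-day episodes and all 7-day ones. The documents do not settle this, so the uniform model is an illustration.

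**Short neutropenia is partly excluded.** Grade 3 ANC under 72 hours is not a DLT, so missing such an episode does no harm.

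**Stronger readings are tempting but unsupported.**
- A reader might infer that a Day 36 abnormality cannot be attributed to the virus. The DLT rule accepts a possible relation and excludes only events due solely to atezolizumab, so it can count. Applied as written, that ambiguity could even add DLTs.
- A reader might infer that there is no virus-only value at all. Day 8 is one; what is missing is a later one.
- A reader might take the worst case as the expected effect. The 84.9% requires every DLT to be a silent 7-day laboratory event. The one intratumoral DLT described in Section 5.2 was clinical, an oral cavity fistula.
- A reader might carry over the IV experience ("Grade 3-4 AEs deemed at least possibly related to protocol therapy were: neutropenia (n=10); thrombocytopenia (n=5"), among 45 patients) as a rate to expect here. Those doses went up to 10¹¹ TCID50, 100 times the top dose level of 10⁹. The lymphopenia in half of six intratumoral patients is reported without grade.

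**Conclusion.** The gap is a fact of the schedule: Table 1 and footnote 9 agree, and nothing else in the protocol fixes a safety panel between Day 8 and Day 36. Silent laboratory DLTs of about a week or less can be missed and counted as no DLT. Under uniform onset over Days 2-36, the planned draws see 38% of 7-day episodes.

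The consequence for dose escalation depends on an unknown, the share of DLTs that are silent laboratory events. With 25% to 50% silent, a true rate of 33% and 7-day episodes, the chance of escalating is roughly 10 to 21 percentage points above its full-detection value (53.5 − 43.4 = 10.1; 64.1 − 43.4 = 20.7). The true rate, onset pattern, duration and silent share are all assumptions.

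For Day 36 abnormalities the supported statement is the limited one: they can be called DLTs, but without a virus-only value after Day 8 the call between MV-NIS and atezolizumab rests on the investigator's judgement and can err in either direction.

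**What to change.** 1. Add hematology and serum chemistry to the Day 15 column of Table 1 and to footnote 9, drawn before the infusion with the blood already collected.
2. Name this as the last virus-only value to be consulted when DLTs are attributed.
3. In Section 13.1.5, tabulate laboratory toxicity separately for Day 1-15 and Day 15-36.
4. State as a limitation that short events starting after Day 15 can still be missed.

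The cost is a Table 1 amendment, two more tubes per patient at an existing visit, and a few more abnormalities to follow up.

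A further draw between Day 15 and Day 36 is optional and should not be presented as closing the remaining gap. In the Days 2-36 model, a draw at the midpoint (Day 25.5) would recover 5 of the remaining 34 − 15 = 19 onset days for 5-day episodes (26%), 7 of 34 − 20 = 14 for 7-day episodes (50%), and 10 of 34 − 23 = 11 for 10-day episodes (91%).
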